1.3.3 Safety Objectives

- To assess the safety and tolerability, including the incidence of adverse events (AEs) and
 events of hypoglycemia, of dapagliflozin and saxagliptin as add-on to diet and exercise and
 metformin (IR or XR), or insulin, or metformin (IR or XR) plus insulin in pediatric T2DM
 subjects when administered for up to 26 weeks of short-term (ST) double-blind treatment, and,
 separately, up to 52 weeks of total treatment.
- To assess the incidence of diabetic ketoacidosis (DKA) with dapagliflozin and saxagliptin as
 add-on to diet and exercise and metformin (IR or XR), or insulin, or metformin (IR or XR)
 plus insulin in pediatric T2DM subjects when administered for up to 26 weeks of ST doubleblind treatment, and, separately, up to 52 weeks of total treatment.
- To assess measures of growth and maturity and Tanner staging and markers of bone health in pediatric T2DM subjects when administered dapagliflozin or saxagliptin as add-on to diet and exercise and metformin (IR or XR), or insulin, or metformin (IR or XR) plus insulin for up to 26 weeks of ST double-blind treatment, and, separately, for up to 52 weeks of total treatment, and for an additional 52 weeks after the study has been completed and study-related treatment has been discontinued.
- To assess the safety and tolerability of dapagliflozin (or saxagliptin) monotherapy in pediatric subjects who are randomized to withdraw background metformin.

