- Eligible subjects who are receiving active treatment will be grouped into two separate strata for saxagliptin and dapagliflozin, and then randomized 1:1 within each strata to either discontinue background medication with metformin or to continue background medication with metformin. For subjects on active treatment who are randomized to withdraw background treatment with metformin, those who are currently receiving high doses of saxagliptin (5 mg) or dapagliflozin (10 mg) will continue to receive the high doses, whereas subjects who are currently receiving low doses of saxagliptin (2.5 mg) or dapagliflozin (5 mg) will have their doses up-titrated to the high doses (saxagliptin 5 mg or dapagliflozin 10 mg). Subjects in the active treatment arms who are randomized to continue background medication with metformin will continue with their current dose of either saxagliptin or dapagliflozin (Figure 3.1-2).
- Eligible subjects who are receiving placebo will be randomized 1:1:1 to either withdraw background medication with metformin and switch to active treatment with either saxagliptin 5 mg or dapagliflozin 10 mg or to remain on background medication with metformin and continue with placebo (Figure 3.1-2).

Discontinuation of background metformin will occur in an unblinded manner. Exposure to monotherapy in subjects undergoing randomized withdrawal of metformin will last from the start of metformin withdrawal for that subject (following randomization at Week 32 or Week 40) until the end of Week 52, when all subjects will discontinue study medications. After Week 52, all subjects will take the most appropriate medication at the discretion of the treating physician.

Rescued subjects and subjects who discontinue IP will not be eligible for randomized withdrawal of background medication at Week 32 or Week 40.

Subjects with $HbA1c \ge 7.5\%$ at Week 26 and Week 32 and subjects who are receiving background treatment with either insulin only, or insulin+metformin, including those randomized to receive placebo, will continue their randomized study medication assigned after the Week-12 assessment in the double-blind LT treatment period.

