Exploratory analyses for the monotherapy period will include only subjects who are on background medication with metformin and have HbA1c measurement < 7.5% at Week 26 or Week 32. Analyses will be performed using the HbA1c value at the withdrawal baseline. The reference time point to be used as 'withdrawal baseline' will be the closest time point on or before the third randomization. The period starting from this baseline to Week 52 will be referred to as the 'randomized withdrawal period'.

For subjects recruited into the study prior to the study site implementation of the third protocol amendment, participation in the third randomization (with possible withdrawal of background medication with metformin) will be at the subject's discretion.

Adverse events and serious adverse events (SAEs) will be assessed during a Week 56 phone visit.

In case a visit is delayed for any reason, subsequent visits should be scheduled such that an interval of at least 12 weeks is maintained between the:

- Week 14 visit and the Week 26 visit.
- Third randomization (for subjects undergoing third randomization; occurring at the Week 32 or the Week 40 visit) and the Week 52 visit.

If more than 12 weeks elapse between the HbA1c collection at Week 26 and the third randomization at Week 32, or the HbA1c collection at Week 32 and the third randomization at Week 40, the subject should not go through this randomization, as the HbA1c value would no longer be reliable to ascertain eligibility for the third randomization. Short- and long-term period study visits can be delayed by a maximum of 11 months in total. If the duration of IP administration is longer than 52 (+1) weeks, the safety follow-up period should be shortened such that the complete study duration does not exceed 104 weeks (+7 days). A window period of -28 days to +7 days from the original scheduled date will be allowed for the Week-104 visit.

Subjects who discontinue study drug before the end of the study treatment period will enter a non-treatment, follow-up phase, in which subjects will follow their visit schedules with modified assessments until study completion. Subjects will attend a post-study visit at Week 104, for assessment of measures of growth and maturity. This visit should be completed without delay (at 104 weeks (+7 days) from Day 1, regardless of whether any other study visits were delayed.

All subjects with HbA1c > 8.0% at and after Week 26 will be rescued.

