Week 12	85	65 to 92	65 to 113	
Week 14	99	93 to 120		
Week 20	141	121 to 162	114 to 162	
Week 26	183	163 to Week 26/ED (whichever is earlier)	163 to Week 26/ED (whichever is earlier)	2 to Week 26/ED (whichever is earlier)

ED = Early discontinuation from the study.

^a PK/PD assessments include plasma samples for analysis of dapagliflozin, saxagliptin, 5-OH-saxagliptin, FPG and DPP-4 activity.

Table 10 Visit windows for LT period and post-study (Week 104) assessments

Visit	Target Day (LT Day ^a)	Day Range by Type of Assessment	
		Vital signs, Safety laboratory panel, FPG, HbA1c, Height, Weight	Growth and maturation markers, Tanner staging, ECG, Fasting lipid panel
Week 32	225 (43)	LTSTDT to 252 / RWSTDT [only applicable for subjects going through the third randomisation] (whichever is earlier)	
Week 40	281 (99)	253 / RWSTDT +1 [only applicable for subjects going through the third randomisation] (whichever is earlier) to 322	
Week 52	365 (183)	323 to Week 56/ED (whichever is earlier)	LTSTDT to Week 56/ED (whichever is earlier)
Week 104	728	Growth and maturation markers, Tanner staging, Height, Weight, BMI Week 56 + 1 day to Week 104 / date of last contact (if earlier than Week 104)	

ED = Early discontinuation from the study. LTSTDT = LT start date (i.e., day following the last day of the ST period). RWSTDT = randomised withdrawal period start date (i.e., date of first IP dose received in randomised withdrawal period).

^a LT day is the target day counting from the start of the LT period (LTSTDT). Target day is based on counting from Day 1 (date of first IP dose in the study).

Table 11 Visit windows for randomised withdrawal period assessments

Visit	Target Day	Date Range by Type of Assessment	
		Vital signs, Safety laboratory panel, FPG, HbA1c, Height, Weight	Growth and maturation markers, Tanner staging, ECG, Fasting lipid panel
Withdrawal Baseline		The closest available value on or before RWSTDT	
Week 40	281	RWSTDT +1 day to 322 (for subjects who were third randomised at Week 32 only)	
Week 52	365	RWSTDT + 1 day (for subjects who were third randomised at Week 40) or 323 (for subjects who were third randomised at Week 32) to Week 56 visit/ED (whichever is earlier)	RWSTDT to Week 56 visit/ED (whichever is earlier)

ED = Early study discontinuation. RWSTDT = randomised withdrawal period start date (i.e., date of first IP dose received in randomised withdrawal period).

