4.7.7.3 Growth and maturity markers

Summaries of growth and maturation markers (see Section 3.4.9) in SI and conventional units will be based on observed data, regardless of rescue medication initiation. Descriptive summaries of absolute values and changes from baseline (where applicable) will be provided for baseline, Week 26, Week 52, and for the post-study visit at Week 104 using the LOCF approach. For the Week 104 analyses, change from Week 52 will also be presented.

In addition, growth and maturation markers will also be summarised during the randomised withdrawal period using the Randomised Withdrawal Subjects Data Set for the first two treatment comparisons described in Section 4.1.5. Descriptive summaries of absolute values and changes from withdrawal baseline (where applicable) will be provided for withdrawal baseline, Week 52 and Week 104 using the LOCF approach.

A categorical change from baseline summary will also be produced by treatment group, age category (≥ 10 and < 15 years, ≥ 15 and < 18 years) using the randomisation strata, and puberty status at Week 26, Week 52 and Week 104 (as defined in Appendix Section 8.10.3) for Week 26, Week 52, and for the post-study visit at Week 104 using the LOCF approach. Similarly, a categorical change from withdrawal baseline summary will also be produced for the Randomised Withdrawal Subjects Data Set for Week 52 and Week 104 using the LOCF approach.

A listing of the growth and maturation markers along with the Tanner stages by subject will be provided. For the ST+LT period this listing will include all data collected up to the end of the LT period. For the ST+LT + Week 104 period, the listing will include all data collected up to Week 104.

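### The safety objective states 52 weeks off treatment, but the Week 104 marker changes pool children with about 4 to more than 52 weeks off drug

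*SAP*

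**What the plan says.** The growth and bone objective in Protocol 1.3.3 covers the treatment period and then runs "for an additional 52 weeks after the study has been completed and study-related treatment has been discontinued". Protocol 3.1 has dosing continue "until the end of Week 52, when all subjects will discontinue study medications".

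The same section then provides for delay: "Short- and long-term period study visits can be delayed by a maximum of 11 months in total". If dosing goes beyond 52 (+1) weeks, "the safety follow-up period should be shortened such that the complete study duration does not exceed 104 weeks (+7 days". The Week 104 visit is due at a fixed time from Day 1, "regardless of whether any other study visits were delayed". On its timing the section says two things. One sentence reads "A window period of -28 days to +7 days from the original scheduled date will be allowed for the Week-104 visit"; another gives 104 weeks with only a +7-day allowance.

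For growth and maturation markers, SAP 4.7.7.3 states "For the Week 104 analyses, change from Week 52 will also be presented", and SAP 4.7.7.4 repeats this for bone biomarkers. Table 10 in SAP 4.1.7.1 assigns values to Week 104 over the range "Week 56 + 1 day to Week 104 / date of last contact (if earlier than Week 104". SAP 4.1.5 groups Week 104 data by first and by last treatment received, with a repeat for children who had the visit. SAP 4.1.7 applies no cut-off dates to Week 104 analyses. None of these refers to time since last dose.

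Two related outputs are handled differently. Height velocity (SAP 8.10.2), which feeds puberty status, uses the actual days between measurements. Weight, height and BMI (SAP 4.7.6) are summarised as change from baseline, with z-scores adjusted for age at assessment and sex.

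**The concern.** Given the objective, a reader will take the Week 52 to Week 104 marker change as what happens over a year off drug. A child whose dosing ran late may be sampled only a few weeks after the last dose. That child contributes a value close to an on-treatment one and, if the marker moves slowly, a change close to zero. The average off-treatment change is then pulled toward zero, and a reversible effect could look persistent.

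The opposite case sits in the same column. A child who stopped drug at Week 26 is 104 - 26 = 78 weeks off drug at Week 104. A Week 52 sample from that child is already off drug, so the change compares two off-treatment values. These are the trial's off-treatment data on growth and bone markers in children, and the planned tables would not show how mixed the intervals are.

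**Working it through.** **Inputs.** End of treatment at Week 52, maximum total delay of 11 months, Week 104 counted from Day 1, window of -28 to +7 days (all Protocol 3.1); target days 365 and 728 (SAP Table 10); 48-week follow-up after Week 56 (SAP 1.6). The documents do not define a month; I use 365.25/12 = 30.44 days and show the range for 30 and 31 days.

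**1. The plan's own figure.** With no delay, 104 - 52 = 52 weeks. The SAP target days give (728 - 365)/7 = 51.9 weeks, and 104 - 56 = 48 weeks matches SAP 1.6. The stated figure reproduces.

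**2. Maximum delay.** Weeks off drug at Week 104 = 104 - (52 + delay in weeks).
- 11 x 30.44 = 335 days = 47.8 weeks, so treatment ends at about Week 99.8 and 104 - 99.8 = 4.2 weeks remain.
- With 30-day months (330 days, 47.1 weeks) 4.9 weeks remain; with 31-day months (341 days, 48.7 weeks) 3.3 remain.
- A visit at the +7-day edge adds one week: 5.2 weeks (4.3 to 5.9).

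**3. Smaller delays.**

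| Total delay (months) | Weeks off drug at Week 104 |
|---|---|
| 0 | 52.0 |
| 1 | 47.7 |
| 3 | 39.0 |
| 6 | 25.9 |
| 9 | 12.9 |
| 11 | 4.2 |

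**4. The early edge of the window.** On the calendar, a visit 28 days early after the maximum delay falls 100 - 99.8 = 0.2 weeks after the last dose. Table 10, however, counts a value as Week 104 only from the day after Week 56. Week 56 is planned 4 weeks after Week 52 and moves with it, so such a sample would normally fall in the Week 52 window. The working floor for a value in the Week 104 tables is about 4 weeks, or about 3 if Week 56 uses its ±7-day allowance.

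**5. Illustration of dilution.** Assume that a marker reverses fully and linearly over 52 weeks and that a share p of children has a given delay. The mean change then shrinks by p x (1 - weeks off drug/52).
- 6-month delay: 1 - 25.9/52 = 0.50. For p = 10% the shrinkage is 5%; for p = 20% it is 10%.
- Maximum delay: 1 - 4.2/52 = 0.92. For p = 10% it is 9%; for p = 20% it is 18%.

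The share and the linear course are my assumptions; the documents give neither.

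**The case against.** The strongest reply is that the delay rule is openly stated and the Week 104 outputs are descriptive. Nowhere do the documents call the Week 52 to Week 104 change a test of reversal, and change from baseline is reported beside it. Individual dosing and marker values are listed, and children affected by the pandemic are summarised (SAP 4.2.2), so the interval could be reconstructed. Eleven months is a cap. All of this is true and limits the harm to interpretation. But no planned table performs the reconstruction. The exposure table (SAP 4.3.1) puts everything beyond 365 days in one open band, and the completer repeat selects on having the visit, not on time off drug.

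Three stronger readings are tempting, and the documents do not support them.
- A reader might infer that off-treatment time in the Week 104 tables can fall to almost nothing. The Table 10 rule in step 4 normally prevents this.
- A reader might infer that every growth output has the same fault. Height velocity already uses actual days, and SAP 4.7.6 plans no change from Week 52 for weight, height or BMI.
- A reader might take 10% to 18% as the expected dilution. It depends on the assumed share and on linear reversal; if a marker returns to its off-drug level within a few weeks, dilution is close to zero.

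It might also seem natural to restrict the main table to children with long intervals. That would select on treatment completion and delay after randomisation and weaken the comparison with placebo.

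**Conclusion.** The point holds for the growth, maturation and bone marker tables. The objective states 52 weeks off treatment, while the visit rules allow about 4 weeks at the extreme (3.3 to 4.9 by month length, at the nominal Week 104 date) and about 26 after a 6-month delay. The Week 52 to Week 104 marker change is neither scaled to nor split by that interval, so one column can span about 4 to more than 52 weeks off drug. The calendar result rests only on the protocol's rules and the length of a month. The size of any dilution cannot be stated, because the share of children delayed is not given. The primary and secondary efficacy analyses are unaffected.

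**What to change.** 1. In SAP 4.7.7.3 and 4.7.7.4, derive weeks from last dose to the Week 104 assessment for each child and tabulate them by arm, in the groupings that SAP 4.1.5 already uses.
2. Add a supportive repeat of the Week 52 to Week 104 marker tables by pre-set bands of that interval, for example under 26, 26 to under 39, and 39 weeks or more. The interval needs a real Week 104 sample date, so base the repeat on observed rather than carried-forward values. Keep the all-children table as the main one.
3. Reword the objective in Protocol 1.3.3 to say up to 52 weeks off treatment.
4. Reconcile the two statements in Protocol 3.1 on the timing of the Week 104 visit.

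The cost is one variable from dates already collected, some extra descriptive tables, and small numbers in some bands. Week 104 has its own database lock (SAP 1.6) and is reported separately (Protocol 9.3), so the additions can be confined to that report.

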3.4.9 Measures of growth and maturity

Measures of growth and maturity include Tanner staging and central laboratory evaluations of growth and maturation markers and bone biomarkers. These will be assessed during the lead-in visit (Tanner staging only) or Day 1 prior to first dose (growth, bone and maturation markers only), and at Week 26, Week 52, Week 104, and (if applicable) at the ETD, Rescue and non-treatment follow-up visits.

Tanner staging is a measure of pubertal development rated on a scale of stage 1 to stage 5 (for details see Appendix Section 8.10.1). Tanner staging will be determined based on investigator assessment and the subjects' self-reports.

Growth and maturation markers

- Thyroid-stimulating hormone (TSH),
- Free thyroxine (assessed at Screening if TSH is abnormal),
- Luteinising hormone (LH) (females only),
- Follicle-stimulating hormone (FSH) (females only),
- Oestradiol (females only),
- Total testosterone (males only),
- Insulin-like growth factor-1 (IGF-1),
- Insulin-like growth factor binding protein-3 (IGFBP-3),
- Calcitonin,
- 25-hydroxy vitamin D.

Bone biomarkers

- Bone alkaline phosphatase,
- Osteocalcin,
- Parathyroid hormone (PTH),

- Carboxyterminal cross-linked telopeptide of Type 1 collagen (CTX-1).

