4.7.7.2 Puberty status

Puberty status (as defined in Appendix Section 8.10.3) will be summarised regardless of rescue medication initiation at Week 26 and Week 52, where the height velocity is based on change from baseline, and Week 104, where the height velocity is based on change from Week 52.

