4.7.7.4 Bone biomarkers

Summaries of bone biomarkers (see Section 3.4.9) in SI and conventional units will be based on observed data, regardless of rescue medication initiation. Descriptive summaries of absolute values and changes from baseline (where applicable) will be provided for baseline, Week 26, Week 52, and for the post-study visit at Week 104 using the LOCF approach. For the Week 104 analyses, change from Week 52 will also be presented.

In addition, bone biomarkers will also be summarised as above for subjects going through the third randomisation using the Randomised Withdrawal Subjects Data Set for the first two treatment comparisons described in Section 4.1.5.

A categorical change from baseline summary will also be produced by treatment group, age category (≥ 10 and < 15 years, ≥ 15 and < 18 years) using the randomisation strata, and puberty status at Week 26, Week 52, and Week 104 (as defined in Appendix Section 8.10.3) for Week

26, Week 52, and for the post-study visit at Week 104 using the LOCF approach. Similarly, a categorical change from withdrawal baseline summary will also be produced for the Randomised Withdrawal Subjects Data Set for Week 52 and Week 104 using the LOCF approach.

A listing of the bone biomarkers along with the Tanner stages by subject will be provided. For the ST+LT period this listing will include all data collected up to the end of the LT period. For the ST+LT + Week 104 period, the listing will include all data collected up to Week 104.

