8.10.3 Puberty status

Puberty status will be defined, by visit, using the Tanner stage at that visit along with height velocity (as defined Section 8.10.1) as follow:

- Early/mid puberty: Tanner stage 1 or Tanner stage 2 or Tanner stage 3, or Tanner stage 4 with height velocity $\geq 1.5 \text{ cm}/26 \text{ weeks} = \geq 3 \text{ cm}/52 \text{ weeks}$,
- Late puberty and young adult: Tanner stage 4 with height velocity $< 1.5 \text{ cm}/26 \text{ weeks} = < 3 \text{ cm}/52 \text{ weeks}$, or Tanner stage 5.

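### The marker tables split by puberty status group children after randomisation, so differences between arms inside a cell can be masked or distorted; a version by baseline Tanner stage should be added

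*SAP*

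**What the plan says.** SAP 4.7.7.3 first plans descriptive summaries of growth and maturation markers by arm, with no puberty grouping. It then adds a second table: "A categorical change from baseline summary will also be produced by treatment group, age category", with age fixed at its Day 1 stratum, and puberty status taken after baseline ("using the randomisation strata, and puberty status at Week 26, Week 52 and Week 104"). SAP 4.7.7.4 repeats the arrangement for bone biomarkers ("using the randomisation strata, and puberty status at Week 26, Week 52, and Week 104").

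SAP 8.10.3 gives the grouping rule: "Puberty status will be defined, by visit, using the Tanner stage at that visit along with height velocity". Stages 1 to 3 are always early/mid puberty and stage 5 is always late. Velocity matters only at stage 4, where the cut is 1.5 cm per 26 weeks, stated as equal to 3 cm per 52 weeks. SAP 4.7.7.2 sets the velocity window: for Weeks 26 and 52 it is the one "where the height velocity is based on change from baseline", and for Week 104 it runs from Week 52. That section also reports puberty status as a result in its own right.

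Tanner stage before treatment is available. SAP 3.4.9 places the first staging at the lead-in visit, and SAP 4.7.7.1 already presents later Tanner results according to baseline status.

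**The concern.** Within a cell such as early/mid puberty at Week 52, the children on drug and on placebo were not put there by randomisation. They were put there by how far they had matured and, at Tanner 4, by how fast they had grown since baseline. If a drug slows growth, some Tanner 4 children who would have counted as early/mid on placebo count as late on drug. Each cell then sets side by side children selected to have similar growth, and a marker that follows growth can look more alike in the two arms than it is.

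Growth, maturity and bone health are a stated safety objective (Protocol 1.3.3), and changes in growth are an adverse event of special interest (SAP 3.4.1). This is also the only planned by-arm marker table that separates children by developmental stage, so a reader looking for an effect confined to growing children would turn to it. Nothing in the SAP warns that its cells are not randomised comparisons.

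**Working it through.** The documents state no figure for this point, so the grouping rule was checked first and its possible effect then illustrated. Every input in steps 2 and 3 is an assumption; the documents give no height velocities, stage mix or marker slopes.

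**Step 1. The cut-off.** 1.5 cm / 183 days x 365 days = 2.99 cm. The stated equivalence with 3 cm per 52 weeks holds.

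**Step 2. Tanner 4 children alone.** Assume placebo velocity is normal with mean 3 and SD 1.5 cm/year, and the drug lowers the mean by 1.0 or 0.5. With a = (3 - mean)/SD, the mean above the cut is mean + SD x φ(a)/(1 - Φ(a)), and below it is mean - SD x φ(a)/Φ(a).

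- Placebo: a = 0; share above the cut 0.500; means 4.197 and 1.803.
- Slowing 1.0: a = 0.667; share above 0.252; means 3.898 and 1.359. Differences from placebo are 0.299 above the cut and 0.444 below it, against a true 1.0.
- Slowing 0.5: a = 0.333; share above 0.369; means 4.032 and 1.602. Differences are 0.165 and 0.201, against a true 0.5.

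The SAP never tabulates Tanner 4 alone: the early/mid cell pools it with stages 1-3, and the late cell with stage 5. These figures show the mechanism, not the size in any reported cell.

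**Step 3. The cells as the SAP forms them.** A simulation of 400,000 children per setting, the same children with and without drug. Assumptions: Tanner 4 share 20%, 35% or 50%, the rest split equally between stages 3 and 5; velocity mean 6/3/1 and SD 2/1.5/0.7 cm/year at stages 3/4/5; slowing of 0.5 or 1.0 cm/year at stages 3 and 4 only; correlation of marker with velocity 0.3 or 0.6; Tanner stage unaffected by drug; marker effect wholly through velocity. The two cell differences were averaged with the untreated split as weights and divided by the true overall difference. If no child changed cell, this ratio would be 100%.

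One setting worked through (Tanner 4 share 35%, slowing 1.0, correlation 0.6): the share of children who move is 0.35 x (0.500 - 0.252) = 8.7%. The true difference is -0.160 SD; the early/mid cell shows -0.143 and the late cell -0.029. The average is 0.5 x (-0.143) + 0.5 x (-0.029) = -0.086, and 0.086/0.160 = 54%.

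| Tanner 4 share | Children who change cell (slowing 0.5 / 1.0) | Within-cell difference kept (slowing 0.5 / 1.0) |
|---|---|---|
| 20% | 2.6% / 5.0% | 64% / 69% |
| 35% | 4.6% / 8.7% | 48% / 53-54% |
| 50% | 6.5% / 12.4% | 38-39% / 44% |

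The correlation hardly alters the ratio. The full range is 38-69%. The summary without puberty groups recovers 100%, because no child can change group in it.

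**Step 4. Direction.** Steps 2 and 3 follow only the velocity route. A drug that delayed Tanner progression would act the other way: a slow-growing child who would have reached stage 4 and been classed late stays at stage 3 and is classed early/mid. That adds slow growers to the early/mid cell on drug and could exaggerate a difference there. The net direction is therefore not fixed.

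**The case against.** The strongest reply is that this is one added descriptive table among several. SAP 4.7.7.3 and 4.7.7.4 open with by-arm summaries of the same markers that do not use puberty status. Height with its age- and sex-adjusted z-score (SAP 4.7.6), Tanner shifts by baseline status (SAP 4.7.7.1) and puberty status itself (SAP 4.7.7.2) are all reported directly. No test or decision rule attaches to the table. Table 24 lists it only in the withdrawal and Week 104 columns, although 4.7.7.3 and 4.7.7.4 name Weeks 26 and 52 as well. All of this stands.

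It rules out two readings a reader might be tempted by. One is that the plan conceals a growth effect; an effect that moved children between cells would still appear in the ungrouped summaries. The other is that this is the table designated to detect harm; no section gives it that role.

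Two more objections stand in part. Velocity reclassifies only Tanner 4 children, and at Week 104 it covers a period after study drug has stopped, so the grouping is not on-treatment at every visit. It is still post-randomisation at every visit. Grouping by current stage also has a rationale, since marker values depend on the child's stage when sampled. That supports keeping the table as a description, but not reading across arms within it.

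The ungrouped summaries do not fully answer the point, because they pool children aged 10 to below 18 at all Tanner stages and cannot show whether an effect is confined to those still growing.

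**Conclusion.** The puberty-status marker tables group on a variable that is defined after randomisation and that treatment can move. Differences between arms inside a cell can therefore be masked or distorted, in either direction. Under the assumptions of step 3, within-cell differences keep roughly 40-70% of the true difference and 2.6-12.4% of children change cell. Those figures assume that the marker effect runs wholly through height velocity and that Tanner stage is unaffected. They may not apply to markers such as TSH, calcitonin, vitamin D or PTH, and they describe means, whereas the planned table is categorical. They illustrate the problem and do not estimate it.

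A reader might infer that the table is always biased towards no difference. The documents do not support that, because the Tanner route can act against the velocity route. The point is a limited improvement to one descriptive table.

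**What to change.** In SAP 4.7.7.3, 4.7.7.4 and Table 24, add the same by-arm categorical change-from-baseline summary grouped by baseline Tanner stage from the lead-in visit (1-3, 4, 5), within age stratum where numbers allow. Name it as the stage-specific view for reading across arms, next to the unstratified summary, which stays the main one. Keep the table by current puberty status, with a footnote that the grouping is defined after randomisation and is not suited to comparing arms. Baseline Tanner stage is the practical choice: puberty status under 8.10.3 cannot be derived at baseline for stage 4, because no height velocity before baseline is defined.

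While editing, correct the cross-reference in 8.10.3, which points to 8.10.1 for height velocity; the definition is in 8.10.2.

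The cost is SAP wording and one more descriptive table from data already collected. Some cells will be sparse: three stages by two age strata give six cells, and 81 / 6 = 13.5 children per cell on average in each arm, fewer for the single-sex hormones. Baseline stage may also differ from the child's stage at sampling, which is why the current table is worth keeping.
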